For assessment of passive glenohumeral internal rotation, participants laid supine with 90° of shoulder abduction in the frontal plane and the elbow flexed at 90°. ¹¹ The examiner stabilized the scapula with one hand by applying mild pressure to its anterior aspect (coracoid process), while applying with the other hand a passive movement of shoulder internal rotation to its maximal point. An assistant read the measurement placing the goniometer with the stationary arm parallel to the floor and the mobile arm in alignment with the forearm starting at the olecranon.³⁹ The same starting posture and goniometer positioning will be used for measuring passive glenohumeral external rotation.

Experimental conditions (independent variables)

There are two independent variables in the research design: treatment condition and time (pre-, post-application). Treatment condition has three levels, which include the AP shoulder mobilization, a manual contact and a no-contact condition.⁴⁷ These experimental conditions will be administered in random order in three separated sessions to all participants, with each session separated by 48 h in order to control for carry-over effects.³⁵ The treatment allocation sequence will be randomized using sealed envelopes and concealed from the investigator who took the outcome measurements. An experienced physiotherapist with a Master degree on manual therapy and more than 10 years of working experience will apply all conditions. This physiotherapist will be blinded to the results of the measurements and questionnaires used as outcome measures.

All conditions will be applied for a total of 10 min, comprising three sets of 3 min, alternating with 30-s rests. Verbal instructions and positioning will be strictly standardized during all the sessions.

Treatment condition

The treatment condition consist on the application of a passive rhythmic AP mobilization to the glenohumeral joint of the affected shoulder. In particular, a Grade III AP glide to the humeral head with the arm positioned in 90° of glenohumeral abduction and full internal rotation was used.⁴⁷ The posterior gliding force to the humeral head was applied maintaining the glide at right angles to the plane of movement and at a frequency of 2 Hz which will be controlled by means of a metronome. The arm will be returned to its original position between each set.

Manual contact condition

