Descriptive statistics will be calculated to describe baseline data. A two-way analysis of variance (ANOVA) through a General Linear Model and appropriate post-hoc tests of simple effects will be used to evaluate hypothesis that AP mobilization produced more changes than manual contact and no-contact conditions from pre- to post-intervention ($P=0.05$). The between subject factor will be treatment condition (AP mobilization, manual contact, no-contact) with time (pre and post-intervention) as within subject factors.

Sphericity will be confirmed by means of Mauchly's test. Bonferroni test will be used for multiple comparisons and the effect size will be estimated using Eta square (η^2) when significant. An effect size of 0.01 will be considered small, 0.06 medium and 0.14 large.⁷

REFERENCES

7. Cohen J. *Statistical Power Analysis for the Behavioral Sciences.* New York, NY: Routledge Academic, 1988.

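### Post-hoc simple effects leave open whether AP is ever compared with a control; read as pre-post tests within each condition, they cannot support the stated hypothesis

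*Protocol*

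**What the plan says.** The Statistical analysis section of the Protocol states the aim of the test, which is to "evaluate hypothesis that AP mobilization produced more changes than manual contact and no-contact conditions from pre- to post-intervention". The tools named for this are in the same sentence: "A two-way analysis of variance (ANOVA) through a General Linear Model and appropriate post-hoc tests of simple effects will be used". It then adds that "Bonferroni test will be used for multiple comparisons", without saying which comparisons form the family. The treatment-by-time interaction, change scores and pairwise contrasts of change are not named.

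On design, the section on experimental conditions says: "Treatment condition has three levels, which include the AP shoulder mobilization, a manual contact and a no-contact condition". It continues: "These experimental conditions will be administered in random order in three separated sessions to all participants". The Statistical analysis section nevertheless says that "The between subject factor will be treatment condition". That label is a separate error, and it matters here only because the remedy uses within-participant contrasts.

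**The concern.** The hypothesis makes two pairwise claims about change: AP against manual contact, and AP against no contact. The comparison with manual contact is the one that separates mobilization from touch and attention, because the therapist uses the same contact point with minimal pressure.

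The ANOVA's interaction can show that change differs somewhere among the three conditions, but not where. The follow-up has to locate the difference, and simple effects can mean two things:

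- **Reading 1:** pre versus post within each condition.
- **Reading 2:** conditions compared with each other at one time point, in practice post-test.

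Reading 1 contains no comparison between conditions. Setting three pre-post p-values side by side can seem to favour AP over a manual contact that changed just as much. It can also miss a real AP advantage because both conditions improve significantly. A significant interaction does not prevent this, since no-contact alone may have produced it.

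**Working it through.** **Inputs.** From the Protocol: three conditions, two time points, every participant receiving all conditions in random order, and significance at 0.05. The Protocol gives no sample size, SD or correlation, so there is no figure of its own to reproduce. Everything numerical below is assumed; the algebra is not.

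**Algebra.** For condition c, let D_c = post_c − pre_c, signed so that improvement is positive. The hypothesis is E[D_AP − D_manual] > 0 and E[D_AP − D_none] > 0.

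- Interaction: (3 − 1)(2 − 1) = 2 df. It tests whether the three D_c are equal.
- Reading 1: each D_c is tested against zero, so no difference between conditions is estimated.
- Reading 2: post_AP − post_manual = (D_AP − D_manual) + (pre_AP − pre_manual). With randomised order and no carry-over, the last bracket has expectation zero. The target is therefore the same expected effect; only the variance differs.

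**Small example for reading 1** (assumed n = 30, SD of change 10, independent changes). The SE is 10/√30 = 1.83. An AP change of 4.0 gives t = 2.19, p = 0.037. A manual contact change of 3.5 gives t = 1.92, p = 0.065. The difference of 0.5 has SE 1.83 × √2 = 2.58, so t = 0.19, p = 0.85. One result is significant and the other not, with almost no difference between them.

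**Simulation.** There were 40,000 trials per setting. Values were normal with SD 1, n = 20, 30 or 40, correlation within a session 0.7-0.95, correlation between sessions 0.5-0.8, and correlation between changes 0 or 0.3. Both readings were applied only after a significant within-participant interaction at 0.05. Reading 1 counts AP significant in the favourable direction and manual contact not significant. The change contrast is a paired t-test on D_AP − D_manual, two-sided, without that gate; only results favouring AP are counted. Mean changes are in SD-of-change units, and ranges run over the correlation settings.

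*All three conditions change by 0.4:* reading 1 favours AP in 1.4-1.8% of trials.

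*AP 0.5, manual contact 0.5, no-contact 0 (no true AP advantage over manual contact); % of trials favouring AP:*

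| Follow-up | n = 20 | n = 30 | n = 40 |
|---|---|---|---|
| Reading 1, level 0.05 | 7.9-9.9 | 7.3-9.4 | 5.3-7.2 |
| Reading 1, level 0.05/3 | 9.8-11.1 | 11.4-13.4 | 10.2-12.4 |
| Reading 2 | 0.9-2.2 over all n | | |
| Change contrast, level 0.05 | 2.3-2.7 over all n | | |

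*AP 1.0, manual contact 0.5, no-contact 0 (a true AP advantage); % of trials finding it:*

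| Follow-up | n = 20 | n = 30 | n = 40 |
|---|---|---|---|
| Reading 1, level 0.05 | 33.3-39.5 | 22.6-24.7 | 12.8-13.6 |
| Reading 1, level 0.05/3 | 47.4-55.2 | 38.4-41.2 | 25.1-26.1 |
| Reading 2 | 8.5-38.6 | 12.6-57.4 | 15.9-71.0 |
| Change contrast, level 0.05 | 31.8-43.7 | 46.0-61.6 | 58.5-74.5 |
| Change contrast, level 0.025 | 21.7-32.0 | 34.4-49.4 | 46.7-63.8 |
| Readings 1 and 2 disagree | 29.0-39.3 | 27.9-47.2 | 23.4-61.7 |

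Reading 1 finds the advantage less often as n grows, because manual contact also becomes significant. Bonferroni over the three pre-post tests raises the false pattern, since it makes a non-significant manual contact result more likely.

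**Precision of reading 2.** With changes uncorrelated between sessions, the post difference has variance 2(1 − r_between) and the difference in change has 4(1 − r_within). The post comparison is the more precise when r_within < (1 + r_between)/2. At r_within = 0.8 and r_between = 0.7 the variances are 0.6 and 0.8, and at n = 30 reading 2 finds the advantage in 55.6% of trials against 46.0-46.8% for the change contrast. At 0.95 and 0.5 they are 1.0 and 0.2, and the order reverses.

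**The case against.** A reader might infer that the planned analysis cannot test the hypothesis at all, or that no simple effect bears on it. The Protocol does not support that. A two-way ANOVA contains the interaction, which tests differential change even though it is not named. Reading 2 is unbiased for the same expected effect under randomised order without carry-over, keeps its error rate and can be the more powerful choice. This stands, and it confines the fault to reading 1 and to the plan leaving both readings open.

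Time has only two levels, so Bonferroni for multiple comparisons may most naturally mean pairwise comparisons of conditions, which is reading 2. That is plausible, but the text does not say so, and the adjustment could equally attach to three pre-post tests.

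Nor does the Protocol say that AP will be called superior because its pre-post test is significant and that of manual contact is not. That rule is assumed here, so the error rates show what reading 1 permits, not what the plan prescribes. Even under that rule the false pattern is rare when all conditions change equally, and at n = 20 the rule finds a true advantage about as often as the contrast, or more often with Bonferroni.

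The interaction gate in the simulation is within-participant, whereas the plan labels treatment a between-participant factor. With a gate on 3(n − 1) df and changes correlated 0.3, the unadjusted false pattern falls from 9.8, 9.2 and 6.9% to 5.9, 6.1 and 5.0% for n = 20, 30 and 40. With uncorrelated changes it barely moves. The upper ends of the unadjusted ranges therefore do not describe the plan exactly as written.

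Finally, exact contrasts are often left to a statistical analysis plan. That would answer an omission. Here the Protocol itself names a follow-up, in the same sentence as a hypothesis that one of its ordinary meanings does not address.

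**Conclusion.** The concern holds in limited form. The follow-up is named, but one ordinary meaning of it never compares AP with a control, and the Protocol does not exclude that meaning. Under the assumed inputs and the assumed decision rule, it favours AP over an equally effective manual contact in about 5-13% of trials when only no-contact differs, against about 2.5% in that direction for a direct contrast. At n = 40 it finds a true advantage in about 13% of trials unadjusted (about 25-26% with Bonferroni over three), against about 58-75% for the unadjusted contrast.

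The harm is not uniform: about 1.5% false patterns when all three conditions change equally, and no loss of power at n = 20. The other meaning, conditions compared at post-test, is a valid comparison whose precision relative to a change contrast depends on correlations that the Protocol does not give. The two meanings disagreed about AP versus manual contact in roughly 23-62% of simulated trials with a true advantage, so the choice should be fixed before the data are analysed. The algebra needs no numerical assumptions; every percentage does.

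**What to change.** In the Statistical analysis section:

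- Name the treatment-by-time interaction as the overall test that change differs among conditions.
- Replace simple effects, as the test of the hypothesis, with two within-participant contrasts of change: AP minus manual contact and AP minus no contact. Give each an estimate and 95% CI, and apply Bonferroni over the two.
- Keep pre-post tests within each condition as description only.
- Correct the adjoining statement that treatment is a between-participant factor. It is a separate error, but the contrasts cannot be within-participant while it stands.

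The cost is the rewording of two adjacent sentences and slightly more analysis work, with no extra data, visits or participants. In some correlation settings the change contrast will have less power than a post-test comparison.

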During the manual contact condition the therapist positione the patient in a mid-range position of glenohumeral abduction and internal rotation and apply the hands to the same contact point as in the treatment condition. However, a simulated posterior glide will be performed but with minimal pressure actually applied.⁴⁷ The number of repetitions and sets were as per the treatment condition.

No-contact condition

During the no-contact condition, the subject remain in the initial starting position thorough the entire session but there are no manual contact between the therapist and the participant.⁴⁷ The total treatment time will be the same as per the other conditions.

Procedure

At the first session and after recording demographic data, the NRPS and DASH will be administered followed by PPT, ROM and muscle strength measurements in a standardized order. Subjects then will received the assigned intervention for that session and, immediately afterwards, all outcome measures will be reassessed following the same order as before. The only exception was the DASH, which will be assessed before and 24 hours after each experimental condition. This procedure will be repeated for all the three test sessions.

An investigator, will blinded to the allocated intervention, performed all the outcome measures before and immediately after the application of the three experimental conditions. Discussion between researchers and subjects will be minimized during treatment in order to facilitate subject blinding and reduce potential interactions. No feedback will be given on performance until after the final session. The extent of subject blinding will be assessed through a short, self-administered, post-experiment questionnaire, where participants will be asked to indicate whether they have experienced a physiotherapy treatment in any of the sessions and, if so, in which session.³⁵

Statistical analysis

Data will be analysed using SPSS 22 for Windows. Statistical significance will be set at $p < 0.05$.

Two independent variables will be incorporated into the research design: treatment (AP mobilization, manual contact, no-contact) and time (pre- and post-intervention). Five dependent variables will be considered including PPT, muscle strength, NRPS, DASH (disability/symptom section) and ROM.

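### The condition-by-time ANOVA is a change-score test; within-participant adjustment for each session's pre-value would be more precise by about (1 − r)/2, with r not given in the protocol

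*Protocol*

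**What the plan says.** The design is a three-condition crossover with a baseline in every session. Under Experimental conditions (independent variables): "These experimental conditions will be administered in random order in three separated sessions to all participants, with each session separated by 48 h". Under Procedure, a blinded investigator "performed all the outcome measures before and immediately after the application of the three experimental conditions". For the disability questionnaire: "The only exception was the DASH, which will be assessed before and 24 hours after each experimental condition". Every outcome therefore has a pre-value in each of a participant's three sessions.

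The Statistical analysis section names the model, "A two-way analysis of variance (ANOVA) through a General Linear Model and appropriate post-hoc tests of simple effects will be used", and the hypothesis that "AP mobilization produced more changes than manual contact and no-contact conditions from pre- to post-intervention". It assigns the factors as follows: "The between subject factor will be treatment condition (AP mobilization, manual contact, no-contact) with time (pre and post-intervention) as within subject factors". It mentions no covariate.

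**The concern.** In a crossover, stable differences between people already cancel when conditions are compared within a person. Subtracting the session's pre-value then removes only the variation that pre and post share within that session, and it adds all the error in the pre-value. If the shared part is small, subtraction costs more than it saves. A fitted slope lets the data decide how much of the pre-value to remove.

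At stake is the precision of the AP-minus-manual-contact and AP-minus-no-contact contrasts on change. A real initial effect could be missed although the readings needed to see it have been collected.

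**Working it through.** **Inputs.** From the protocol: three conditions, two time points, all participants in all conditions, a pre-value in each session, significance at 0.05. The protocol states no sample size, power, SD or pre-post correlation, so it has no figure to reproduce. Values of r, n and the SD ratio below are assumptions.

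**Step 1: what is tested.** With two time levels, the condition-by-time interaction equals an ANOVA of post minus pre. On one simulated data set of 15 participants with both factors within-participant, the interaction and the repeated-measures ANOVA of change gave the same F, 4.5992 on 2 and 28 df. With condition between-subject, as written, the interaction is the one-way F on change, 3.258 on the same data. Both readings are change-score analyses.

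**Step 2: variance.** Let s² be the within-participant variance of a session's reading, equal before and after.
- Change contrast between two conditions: 4s²(1 − r)/n
- Contrast adjusted with a within-participant slope: 2s²(1 − r²)/n
- Ratio: (1 − r²)/[2(1 − r)] = (1 + r)/2, so the reduction is (1 − r)/2

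| r (assumed) | Change, in s²/n | Adjusted, in s²/n | Reduction | Simulated, n = 12 | Simulated, n = 31 |
|---|---|---|---|---|---|
| 0 | 4 | 2 | 50% | about 47% | 48–50% |
| 0.25 | 3 | 1.875 | 37.5% | about 34% | 36–37% |
| 0.5 | 2 | 1.5 | 25% | about 21% | 24–26% |
| 0.75 | 1 | 0.875 | 12.5% | 8–9% | about 11% |
| 0.9 | 0.4 | 0.38 | 5% | −1 to +1% | about 4% |

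A separate simulation at n = 12 to 31 gave variance ratios of 0.50–0.55, 0.77–0.80, 0.91–0.92 and 0.96–1.00 at r = 0, 0.5, 0.75 and 0.9. With n = 20 and 30, where the change-score test had about 79% power, adjustment gave about 87% at r = 0.5. Type I error was 4.5–5.4% for both methods.

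**Step 3: unequal variances.** With k = post SD / pre SD, the reduction is (1 − rk)²/(1 + k² − 2rk).
- k = 1.25, r = 0: 1/2.5625 = 39%. At r = 0.75: 0.0625²/0.6875 = 0.6%.
- k = 0.8, r = 0: 1/1.64 = 61%. At r = 0.75: 0.4²/0.44 = 36%.

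**Step 4: how the pre-value enters.** The gain needs a slope fitted on within-participant deviations. Suppose 90% of outcome variance is stable between people. A pooled slope with no participant term then gave only about 10%, 5% and 2.5% at r = 0, 0.5 and 0.75. A random intercept with the raw pre-value (n = 30) gave about 11%, 6% and 3%.

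**Step 5: carry-over.** Let AP leave a sustained shift c. Under random order AP precedes a given control session half the time, so that session's pre- and post-values rise by 0.5c on average. Adjustment removes slope × 0.5c and leaves a bias of −0.5(1 − slope)c in the AP-minus-control difference. If c is 20% of the effect:
- slope 0.5: 0.5 × 0.5 × 20% = 5% of the effect
- slope 0: 0.5 × 1 × 20% = 10% of the effect
- slope 1 (change scores): 0

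**The case against.** **The plan states a change hypothesis and tests change.** This is coherent, and under randomised order the contrast is unbiased. A reader might infer that the comparison is invalid; neither the documents nor the simulated error rates support that. The protocol does, however, fix the model and factors without a covariate, so the choice is not simply left open for a SAP.

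**The size is unknown.** A reader might take a 12–50% saving as the expected gain. That range needs r between 0 and about 0.75 with equal variances, and the protocol supports neither. It averages three readings for PPT and strength, marks and photographs the PPT sites, and describes good repeatability. An r above 0.75 cannot be excluded, and at high r with few participants the gain vanishes. Equally, reliability that includes differences between people does not establish a high r once the person effect is removed.

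**Not every comparison subtracts the pre-value.** A reader might infer that all planned comparisons do. The plan also has simple-effects tests, and a simple effect of condition at post-intervention does not subtract it. The protocol does not say which simple effects are meant, so the point is limited to contrasts on change.

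**The plan as written is not a paired analysis.** Condition is called a between-subject factor, so the (1 − r)/2 comparison is with a paired change-score contrast, not with the literal text. The cost in degrees of freedom also differs. With three conditions, adjustment moves error df from 2n − 2 to 2n − 3 against a paired ANOVA of change, but from 3n − 3 to 2n − 3 against the between-subject version.

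**Change scores protect against sustained carry-over.** This stands. The bias from adjustment is largest at low slopes, where the precision gain is also largest, and the 48-hour separation shows that carry-over was a design concern.

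**Conclusion.** The point holds as one of efficiency. Under either reading of the factor roles, the condition-by-time test forces a slope of 1 on each session's pre-value and brings its error into the AP-versus-control contrasts on change. In large samples a fitted within-participant slope is never less precise. The gain could be substantial or negligible: it depends on r, on n and on the ratio of post to pre SD, none of which the protocol gives.

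The factor wording in the same section is a contradiction in its own right. Condition cannot be a between-subject factor when, as the section on experimental conditions says, "These experimental conditions will be administered in random order in three separated sessions to all participants". The model proposed below removes that contradiction too.

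**What to change.** For each outcome, analyse the post-value (the 24-hour value for the DASH) with condition as a within-participant factor, participant as a fixed block and that session's pre-value as covariate. Report the adjusted AP-minus-manual-contact and AP-minus-no-contact differences with 95% confidence intervals. State that participant enters as a fixed block, because a raw pre-value in a pooled or random-intercept model can lose most of the gain. Delete the between-subject description of condition.

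Keep the paired change-score contrast as a sensitivity analysis, to show whether the result depends on the absence of sustained carry-over.

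The cost is a sentence or two of analysis text and one degree of freedom relative to a paired change-score ANOVA. No new data are needed, and SPSS can fit the model. The Participants section dates data collection to February–March 2018; if outcomes have already been analysed, report the adjusted model and label it as a later addition.

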Previous studies have demonstrated positive effects in terms of improvement of shoulder ROM, pain sensitivity and muscle function (i.e. reduction on rotator cuff muscle activity) when applying an AP mobilization to the humeral head in the form of a mobilization with movement (MWM).^{43,51} Whether similar clinical effects might be obtained with an AP mobilization to the humeral head following Maitland's approach is unknown.

The aim of this study will be investigated the initial effects of a passive rhythmic AP mobilization applied to the glenohumeral joint on pain sensitivity and muscle function in overhead athletes with chronic shoulder pain. In addition, the effects of this technique on self-reported shoulder pain and disability and ROM will be also evaluated.

METHODS

A repeated-measures, double-blinded randomized, placebo-controlled study will be conducted to evaluate the initial effects of an AP mobilization of the glenohumeral joint on pressure pain threshold (PPT), muscle strength, self-reported shoulder pain and disability and ROM.

Participants

The overhead athletes aged between 18-60 years of age will participated in this study. Besides presenting with a history of chronic shoulder pain (i.e. lasting ≥ 3 months), athletes will required to play overhead sport regularly (at least once per week) in an organized way. Recruitment of potential volunteers will be conducted at the Student Sport Center *BLINDED* through poster advertisement. Volunteers who met the inclusion criteria will be then evaluated as they reached the laboratory.

Subjects will be excluded if they had a non-musculoskeletal origin of shoulder pain, previous surgery to the shoulder complex, frozen shoulder, any co-existing inflammatory, infectious or neurological condition that would exclude the patient from physiotherapy treatment, or any evidence of pain referred from the cervical spine to the shoulder.⁵⁵ In addition, they will be instructed to avoid any medication intake during the week prior to the study commencement and for the duration of the study.

Data collection took place at the *BLINDED* from february to march 2018. All participants will received an information leaflet and will gave written informed consent prior to the study beginning. The study was approved by the local Institutional Ethics Committee and all the procedures will be conducted according to the Declaration of Helsinki.

Outcome measures (dependent variables)

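### Treatment condition is specified as a between-subject factor although every participant receives all three conditions, so the treatment-by-time test has the wrong error term and degrees of freedom

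*Protocol*

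**What the plan says.** The protocol describes the design consistently. Methods opens with "A repeated-measures, double-blinded randomized, placebo-controlled study will be conducted". Under Experimental conditions, "Treatment condition has three levels, which include the AP shoulder mobilization, a manual contact and a no-contact condition", and "These experimental conditions will be administered in random order in three separated sessions to all participants". Under Procedure, after the pre and post measurements are set out, "This procedure will be repeated for all the three test sessions". Each participant therefore supplies six measurements per outcome: three conditions, each before and after.

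The Statistical analysis section states the hypothesis as "AP mobilization produced more changes than manual contact and no-contact conditions from pre- to post-intervention", to be tested by a two-way ANOVA. It then fixes the model: "The between subject factor will be treatment condition (AP mobilization, manual contact, no-contact) with time (pre and post-intervention) as within subject factors". It adds that "appropriate post-hoc tests of simple effects will be used", and, of Mauchly's test, "Sphericity will be confirmed by means of" it. Nothing elsewhere in the protocol corrects the factor sentence.

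**The concern.** The factor sentence contradicts the design. A between-subject factor is one on which different people sit at different levels; here the same people sit at all three.

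The section also conflicts with itself. Its only within-subject factor is time, with two levels. Sphericity holds trivially for two levels, so Mauchly's test has nothing to examine unless the three-level treatment factor is within-subject. This suggests that a within-subject analysis was intended, but it is not what is specified.

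The sentence defines the model for all five dependent variables. An analyst who follows it enters three records per person with treatment as a grouping factor, and loses across conditions the advantage of each participant serving as their own control. An analyst who runs the correct model departs from the written plan.

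**Working it through.** **Inputs from the protocol.** Three conditions, two time points, all conditions given to all participants, significance level 0.05, hypothesis about change from pre to post. The protocol gives no sample size, SD, effect size or correlation, so there is no figure of its own to reproduce.

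**Assumptions.** n = 20, 30 or 40; normal change scores with equal variance s² and a common correlation rho between one person's change scores in any two sessions; for power, an effect that the correct within-subject test detects with 80% power.

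**Step 1: reduce to change scores.** With two time points, the treatment-by-time F of the model as written equals a one-way ANOVA on change scores. A numerical check on one simulated data set (n = 20) gave F = 0.1546 by both routes. Stable differences between people cancel in the change score; differences between people in how much they change do not.

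**Step 2: degrees of freedom.** As written: 3n-3. Within-subject: 2(n-1).
- n = 20: 57 versus 38 (critical F 3.16 versus 3.24)
- n = 30: 87 versus 58
- n = 40: 117 versus 78

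**Step 3: error term.** Under the null hypothesis the treatment mean square estimates s²(1-rho), and so does the correct error term. The error term as written averages 2(n-1) df at s²(1-rho) and (n-1) df at s²(1+2rho), which gives s²[2(1-rho) + (1+2rho)]/3 = s². The F ratio as written is therefore centred near 1-rho instead of 1.

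For large n this implies a type I error of about 0.05^(1/(1-rho)): 8.2% at rho = -0.2, 5% at 0, 2.4% at 0.2, 1.4% at 0.3 and 0.25% at 0.5.

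**Step 4: simulation** (100,000 trials per setting; rho = 0.2 from a separate check on pre/post data with 40,000 trials):

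| rho | Type I error as written | Power as written | Sample size |
|---|---|---|---|
| -0.2 | 7.9-8.3% | not computed | n = 20-40 |
| 0 | 5.0% | 81% | n = 20-40 |
| 0.2 | 2.4% | about 72% | n = 30 |
| 0.3 | 1.5-1.6% | 64-65% | n = 20-40 |
| 0.5 | 0.3-0.4% | 43-45% | n = 20-40 |

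The within-subject test stayed at 4.8-5.2% type I error and about 80% power throughout. Independent recomputations agreed within simulation error.

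**Step 5: post-hoc tests.** The protocol does not say which simple effects are meant. If they compare pre with post within a condition, the pairing is kept and there is no further problem. If they compare conditions at the post time point, ignoring the pairing inflates the standard error by 1/sqrt(1-r), where r is the within-person correlation. For assumed r = 0.6 to 0.9 that is 1.58 to 3.16 times. At r = 0.6 and n = 30, power falls from 80% to 41%.

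**The case against.** The strongest reply is that this is a mislabelled factor. The design is unmistakable, and the planned Mauchly test points to a within-subject model, so a competent analyst would probably run the right one. That is plausible, but the factor sentence is the only one that says how the model is set up, and it says the opposite. Nor can it be left to a separate analysis plan, because the protocol fixes the structure and fixes it wrongly.

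Four narrower objections have force:
- **Sign of rho.** Person-level variation in response gives rho of zero or more, and nothing in the protocol points to a negative value. The main expected harm is lost power; the inflated false-positive rate is a less likely case.
- **Sphericity.** The simulations assume it. With one condition's change SD set at 2 or 3 times the others (n = 30, rho 0 or 0.5), the uncorrected within-subject F rejected a true null in roughly 6-7% of trials. The correct test is therefore valid under sphericity or with a correction, and Mauchly's test alone corrects nothing.
- **Simple effects.** The standard-error figures rest on one reading of an open phrase, and that reading is not the stated hypothesis. They are secondary.
- **Size.** Every power and type I figure rests on assumed n and rho. Only the degrees-of-freedom contrast follows from the documents alone.

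**Conclusion.** The specification is wrong as written and must be corrected. The contradiction and the df contrast (3n-3 against 2(n-1)) need no assumption. The practical harm does: it is close to nil at rho = 0, it takes power from 80% to about 65% at rho = 0.3 and to about 44% at rho = 0.5, and at rho = -0.2 it pushes type I error to about 8%. These figures assume n = 20 to 40 and equally correlated change scores of equal variance; they illustrate the harm and do not measure it. Since rho is not known in advance, the test as written cannot be relied on to hold its nominal level. The within-subject test, corrected for non-sphericity where needed, does not depend on knowing rho.

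**What to change.** Replace the factor sentence with: *Treatment condition (three levels) and time (two levels) will both be within-participant factors in a 3 × 2 repeated-measures ANOVA.* Apply Mauchly's test to the treatment and treatment-by-time terms, and use a Greenhouse-Geisser correction, either routinely or when sphericity is doubtful. State that post-hoc comparisons between conditions are paired within participant.

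If a linear mixed model is preferred, a participant random intercept alone is not adequate. In simulations with n = 30, rho = 0, residual SD 1 and participant SD 2, it gave 0.5% type I error and 51% power with a session SD of 1, and 0.03% and 22% with a session SD of 1.5. The model should include participant, participant-by-session and participant-by-time effects or an equally flexible covariance for the six measurements. Modelling the change scores with a participant effect is also sound.

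The cost is the wording of one paragraph and a different SPSS set-up with two within-subject factors. No extra data or participants are needed.
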